**Agreement Table**

		cC		
FS Results	Agree	DisAgree		
	a	b	a+b	
Disagree	c	d	c+d	
		a+c	b+d	n T

The estimate of agreement is  $p_{AG} = (a+d)/n_T$ . It is desired to test the hypothesis that the agreement is greater than 80%. This is compatible with the expected result that both the sensitivity and the specificity will be about 90%. Thus the hypothesis to be tested is that the agreement is 80% (H0: Null hypothesis) versus the alternative hypothesis that the agreement is greater than 80% (HA: Alternative hypothesis).

$$H_0: \pi_{AG} = 80\% \text{ vs } H_A: \pi_{AG} > 80\%$$

Where  $\pi_{AG}$  is the percent agreement between Frozen Section and cCell. This will be tested utilizing the exact binomial test. Estimates of agreement from the pilot study indicate that the agreement will be greater than 86%. In this study, there will be 250 participants available for analysis for the estimation and testing of agreement. For outcome results, if the agreement is 86%, with the sample size of 250, the probability the estimated agreement will be greater than 80% is greater than 90%. That is,  $P(p_{AG} > 80\%) > 90\%$ .

**Sensitivity Table** – Sensitivity is only calculated when the truth standard is positive for tumor.

Agreement Table with Tumor Truth

		cC		
FS Results	Agree w/Truth	Disagree w/Truth		
	e	f	e+f	
Disagree	g	h	g+h	
		e+g	f+h	n T

The sensitivity of the Frozen Section is given by  $p_{SenF} = (e+f)/n_T$  and the sensitivity of cCell is given by  $p_{SenC} = (e+g)/n_T$ . It is desired to demonstrate that the sensitivity of cCell is non inferior to that of Frozen section.

The non inferiority of the sensitivity of cCell result versus the sensitivity of the Frozen Section is given as:

$$H_0: \pi_{SenF} - \pi_{SenC} > \Delta \text{ versus } H_A: \pi_{SenF} - \pi_{SenC} \leq \Delta$$

Here  $\pi_{SenF}$  is the true sensitivity for Frozen Section and  $\pi_{SenC}$  is the true sensitivity for cCell. The parameter  $\Delta$  is the non-inferiority limit. In this study, it is proposed to utilize a  $\Delta=0.05$  (5%). If that  $\Delta$  is used and the anticipated sensitivity for both Frozen Section and cCell is 90%, then

with a sample size of 200 tumor positive samples the probability the difference between the estimated sensitivities is less than 5% is greater than 90%. That is  $P((\pi_{\text{SenF}} - \pi_{\text{SenC}} \leq 5\%) > 90\%.$

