**Specificity Table** – Specificity is only calculated when the truth standard is negative for tumor.

Agreement Table with Non-Tumor Truth

		cC		
FS Results	Agree w/Truth	Disagree w/Truth		
Agree	r	s	r+s	
Disagree	t	u	t+u	
		r+t	s+u	$n_2$

The specificity of the Frozen Section is given by  $p_{\text{SpeF}} = (r+d)/n_2$  and the specificity of cCeLL is given by  $p_{\text{SpeC}} = (r+d)/n_2$ . It is desired to demonstrate that the specificity of cCeLL is non-inferior to that of Frozen section.

The non-inferiority of the specificity of cCell result versus the specificity of the Frozen Section is given as:

$$H_0: \pi_{\text{SpeCF}} - \pi_{\text{SpeC}} > \Delta \text{ versus } H_A: \pi_{\text{SpeF}} - \pi_{\text{SpeC}} \leq \Delta$$

Here  $\pi_{\text{SpeF}}$  is the true specificity for Frozen Section and  $\pi_{\text{SpeC}}$  is the true specificity for cCell. The parameter  $\Delta$  is the non-inferiority limit. In this study, it is proposed to utilize a  $\Delta=0.10$  (10%). If that  $\Delta$  is used and the anticipated specificity for both Frozen Section and cCell is 90%, then with a sample size of 50 tumor negative samples the probability the difference between the estimated specificities is less than 10% is greater than 80%. That is  $P(\pi_{\text{SpeF}} - \pi_{\text{SpeC}} \leq 10\%) > 80\%.$

The sensitivity and the specificity hypotheses will be tested using McNemar's test by constructing an upper 97.5% confidence bound for the difference between the two methods. If the upper bound is less than  $\Delta$  (5% for sensitivity and 10% for specificity) then the two images are said to be non-inferior. The upper confidence bound is given by:

$$p_{\text{FS}} - p_{\text{cC}} + z_{0.05} \text{se}(p_{\text{FS}} - p_{\text{cC}}), \text{ where}$$

$$\text{se}(p_{\text{FS}} - p_{\text{cC}}) = \frac{\sqrt{(b+c)}}{n}$$

The standard error (se) for the difference depends on the number of discordant pairs (a and b). Where a and b correspond to f and g from the sensitivity table and to t and s from the specificity table. The estimates  $p_{\text{FS}}$  and  $p_{\text{cC}}$  correspond to the sensitivity of the Frozen Section,

$p_{\text{SenF}}$ , and the sensitivity of cCell,  $p_{\text{SenC}}$  when sensitivity is being tested and they correspond to the specificity of the Frozen Section,  $p_{\text{SenF}}$ , and the specificity of cCell,  $p_{\text{SenC}}$ , when specificity is being tested.

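### As printed, the specificity non-inferiority rule in Section 8.3.1 cannot yield the specificity difference: one set of symbols belongs to sensitivity, the other always differs by zero

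*Combined protocol and SAP*

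**What the plan says.** Section 8.3.1 sets non-inferiority margins of 0.05 for sensitivity (200 tumor samples) and 0.10 for specificity (50 normal samples). Both hypotheses are to be tested by "constructing an upper 97.5% confidence bound for the difference between the two methods". The decision clause begins "If the upper bound is less than" and compares the bound with the margin. The bound is p_FS − p_cC + z_0.05 × se, with se = √(b+c)/n.

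Three pieces of text then say what goes into that formula.

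- **Specificity estimates as defined.** Under the specificity table, the frozen section estimate is (r+d)/n2. The line continues "r+d)/n_2$ and the specificity of cCeLL is given by" and repeats the same expression, so both methods have one definition. The table's cells are r, s, t and u.
- **Estimates assigned to the bound.** The estimates are the sensitivity pair "when sensitivity is being tested and they correspond to the specificity of the Frozen Section" and of cCeLL. The symbols printed for this specificity case are again p_SenF and p_SenC.
- **Cells in the standard error.** "The standard error (se) for the difference depends on the number of discordant pairs (a and b"; the sentence after it adds "Where a and b correspond to f and g from the sensitivity table and to t and s from the specificity table".

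**The concern.** Section 8.3.1 holds the only operational non-inferiority rule for two of the three primary endpoints. The synopsis gives tables for agreement and sensitivity but none for specificity, and no standard error formula.

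For sensitivity the printed estimates are right: (e+f) and (e+g) over the number of tumor samples, so the difference is (f−g)/n1. For specificity, someone who follows the symbols inserts the sensitivity difference. Someone who notices this and turns to p_SpeF and p_SpeC inserts zero, whatever the data. In both cases the observed specificity deficit drops out of the bound and only the number of discordant normal samples decides the result. A device that misses the margin could be declared non-inferior. The error can also run the other way.

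**Working it through.** **Inputs from the plan.** n1 = 200, n2 = 50; margins 0.05 and 0.10; both methods anticipated at 90%; upper 97.5% bound (z = 1.96), printed multiplier z_0.05 (1.645 as an upper-tail point). The plan gives no discordance rate for tumor or normal samples. I assume 10% to 18%; the upper end is 2 × 0.9 × 0.1 = 0.18, which is independent errors.

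**1. The plan's own figures.** Take the discordant cells as f, g and s, t. At 18% discordance the standard errors are √36/200 = 0.030 and √9/50 = 0.060. The probability that the estimated difference is below the margin is then:

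| | Normal, 18% | Exact, 18% | Normal, 10% | Exact, 10% | Plan |
|---|---|---|---|---|---|
| Sensitivity | 0.952 | 0.944 | 0.987 | 0.983 | above 90% |
| Specificity | 0.952 | 0.934 | 0.987 | 0.978 | above 80% |

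The plan's statements are reproduced, so the intended structure is sound.

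**2. What the specificity difference should be.** Rows of the table are frozen section and columns are cCeLL. The margins give p_SpeF = (r+s)/n2 and p_SpeC = (r+t)/n2, so the difference is (s−t)/n2.

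**3. What the printed routes give.**

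- Through p_SenF and p_SenC: (f−g)/n1, the sensitivity difference. This is zero if the two sensitivities are equal, as the plan anticipates.
- Through p_SpeF and p_SpeC: (r+d)/n2 − (r+d)/n2 = 0 always. Borrowing d from the agreement table does not help, because it cancels.

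**4. Effect on the decision** (assumed counts among 50 normal samples, margin 0.10).

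| Counts | True difference | Bound, true difference | Bound, zero difference |
|---|---|---|---|
| s=6, t=0, z=1.96 | 0.12 | 0.12 + 1.96√6/50 = 0.216, fails | 0.096, passes |
| s=6, t=0, z=1.645 | 0.12 | 0.201, fails | 0.081, passes |
| s=5, t=1, z=1.96 | 0.08 | 0.08 + 0.096 = 0.176, fails | 0.096, passes |
| s=5, t=1, z=1.645 | 0.08 | 0.161, fails | 0.081, passes |
| s=0, t=7, z=1.96 | −0.14 | −0.14 + 1.96√7/50 = −0.036, passes | 0.104, fails |

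With a zero difference inserted, the test passes whenever s+t is at most 6 at z = 1.96 (at most 9 at z = 1.645), whichever method made the errors.

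**5. The multiplier.** At an observed difference of zero and the correct cells:

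| Assumed discordance | Sensitivity, 1.645 / 1.96 (margin 0.05) | Specificity, 1.645 / 1.96 (margin 0.10) |
|---|---|---|
| 10% | 0.0368 / 0.0438 | 0.0736 / 0.0877 |
| 14% | 0.0435 / 0.0519 | 0.0870 / 0.1037 |
| 18% | 0.0494 / 0.0588 | 0.0987 / 0.1176 |

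At 14% and 18% the printed z_0.05 passes both tests and the stated 97.5% level fails both. At 10% both multipliers pass.

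**The case against.** The strongest reply is that the intent can be recovered. The words beside the misprinted symbols say specificity, the hypotheses are written with specificity parameters, and the last step of the synopsis study procedure defines specificity in words in the usual way. An experienced programmer would read (r+s)/n2 and (r+t)/n2 off the table margins. That is fair, and it is why this is a correction to the text and not a flaw in the design. But the reader has to discard both printed routes and rebuild the estimator. The synopsis Analysis Methods do not settle the matter, because there cCeLL specificity is described as the probability of a negative reference given a negative reading, which reverses the conditioning.

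A reader might also infer that the standard error is wrong if programmed as written, because the formula has b and c while the text says a and b, and a is a concordant cell in the agreement table. The documents do not support that. The following sentence maps the letters to f and g and to t and s, which are the true discordant cells. Someone who follows it gets √(f+g)/n1 and √(s+t)/n2. This part is a labelling slip.

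The 6-versus-0 example is chosen to make the flip plain and is not a forecast. The 5-versus-1 case flips as well.

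**Conclusion.** The concern holds for specificity. Neither printed set of symbols produces the specificity difference, and the decision can reverse: with assumed counts of 6 and 0, an observed 12-point deficit against a 10-point margin passes at 0.096 when the correct bound is 0.216. The reversal does not depend on which multiplier is used. The sensitivity estimates and the probabilities stated for both endpoints are correct, and the a/b versus b/c mismatch does not change the standard error.

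The conflict between the 97.5% level and z_0.05 is a further fault in the same rule. It changes the decision at zero observed difference for assumed discordance of 14% and 18%, but not 10%.

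The counts and discordance rates are assumptions, since the plan gives none. The finding also assumes that the formulas in the operative protocol are those in the public document.

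**What to change.** In Section 8.3.1:

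- Define p_SpeF = (r+s)/n2 and p_SpeC = (r+t)/n2, and use these symbols where the specificity estimates are assigned to the bound.
- Print two explicit bounds: (f−g)/n1 + z√(f+g)/n1 for sensitivity and (s−t)/n2 + z√(s+t)/n2 for specificity. Remove the letters a, b and c from this part.
- Use n1 for the tumor total, as the synopsis does. Section 8.3.1 labels it n_T, the symbol of the 250-sample agreement table.
- State z = 1.96 for the 97.5% bound. This also agrees with the two-sided 95% interval in the synopsis.
- Label any discordance rate used for illustration as an assumption.

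The change is to text and programming specifications only; it needs no new samples or procedures. It should be made before the comparative results are seen, because a later repair of a primary decision rule would look data-driven.

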### **8.3.2 Analysis Population**

The analyses described above will be performed on the intent to analyze population. That is, all samples in that are collected and are analyzable by frozen section will be utilized in the analysis regardless of whether they were successfully analyzed by both methods.

A secondary analysis will be done on the primary endpoints on the samples that were analyzable by both methods.

### **8.3.3 Demographic Baseline Data**

Demographic data and other baseline characteristics will be summarized via descriptive statistics.

## **9. Operational Considerations**

### **9.1 Regulatory, Ethical and Study Oversight**

It is the Sponsor's responsibility to ensure that the study is conducted according to ISO 14155, the Declaration of Helsinki, other applicable regulatory requirements, the study protocol, and any conditions of approval imposed by the REB or Health Canada (HC). The Sponsor also will ensure proper clinical site monitoring.

The Sponsor has taken out an insurance policy for the total duration of the study. This insurance policy covers the participants in respect of the risks involved in this study according to this CIP. In the case of injury or disability deriving from participation in the study, the participant is requested to inform the treating physician responsible for the study without delay.

Prior to allowing the sites to start enrolling participants into the study, the Sponsor is responsible for selecting investigators, ensuring REB and HC approvals are obtained where applicable, and signing the Investigator Site Agreement with the investigators and/or hospitals. The study protocol (or amendment[s]), Informed Consent Form, and other applicable study related documents must be submitted to and approved by the REB and HC before enrolment of participants.

A signed copy of the REB approval letter addressed to the investigator must be submitted to the sponsor certifying study approval prior to participant enrolment. The sponsor is responsible for notifying HC of the intention to perform a clinical investigation under this protocol and will ensure an official approval is obtained prior to starting the clinical investigation. The investigation will not start before the required approvals or favorable opinions from the REB and HC have been obtained.

Any substantial amendments to the protocol will require REB and HC approval before implementation of changes made to the study design, except for changes necessary to eliminate an immediate hazard to study participants.

## **9.2 Confidentiality and Privacy**

All materials, information (oral or written) and unpublished documents provided to the participating physician (or any steps taken by the company on their behalf), including, but not limited to, the protocol, eCRFs, and IB are the sole property of the Sponsor.

These materials and information (both global and partial) may not be provided or disclosed by the participating physicians or any person on their team to unauthorized persons without the prior written consent of the Sponsor.

The participating physician considers all information received, obtained, or derived during the study to be confidential and will take all necessary steps to ensure that there is no breach of confidentiality, except for the information to be provided according to law.

The participant's personal data (age, sex, cCeLL images, date of surgery) and participating physician's personal data which may be included in Sponsor database shall be treated in compliance with all local and international applicable laws and regulations. When archiving or processing personal data pertaining to the physician and/or to the participants, Sponsor shall take all appropriate measures to safeguard and prevent access to this data by any unauthorized third-party.

## **9.3 Sponsor Responsibilities**

The sponsor has the overall responsibility for the conduct of the study, including assurance that the study satisfies international standards and the regulatory requirements of the relevant regulatory authorities.

The Sponsor will be responsible for:

- Selection of clinical investigators and sites: The Sponsor will select qualified investigators and facilities which have adequate study population to meet the requirements of the investigation.
- Training of investigators and site personnel and site monitoring: The training of the Investigator and clinical site personnel will be the responsibility of the Sponsor, or designee, and may be conducted during an investigator meeting, a site initiation visit, or other training sessions. Periodic monitoring visits will be conducted frequently enough to ensure that all clinical participant data are properly documented and that the study is properly conducted.
- Documentation: The Sponsor will collect, store, guard and ensure completion of all study relevant documents by the relevant parties.
  - Signed and dated eCRFs
  - Records of any Serious Adverse Events (SAEs) reported to the Sponsor during the clinical investigation

- Any statistical analyses and underlying supporting data
- Final report of the clinical investigation
- Submitting Reports
- Maintaining Records: The Sponsor will maintain copies of correspondence, data, SAEs and other records related to the clinical study according to requirements set forth by ISO 14155 and regulations.
- Monitoring: The Sponsor is responsible for monitoring the study to ensure compliance with ISO 14155 and regulatory requirements.

#### **9.4 Investigator Responsibilities**

- Protocol acceptance: Prior to starting enrolment of participants, the Investigator must read and understand this study protocol, and must sign and date the Protocol Signature page. The Site Agreement documents agreement to all conditions of the study protocol and agreement to conduct the study accordingly. This study will be conducted in accordance the Declaration of Helsinki and other applicable regulatory requirements and standards, and any conditions of approval imposed by the REB or regulatory authorities.
- Required documents: The following documents must be submitted to the Sponsor, or designee prior to participant enrolment:
  1. Signed Protocol Signature Page
  2. Recent ( $\leq$  2 years old) signed and dated English Curriculum Vitae (CV) of the Principal Investigator and co-investigators of the clinical site. The CV should clearly show the Investigator/co-investigators' qualifications and experience.
  3. Copy of the written confirmation of the REB regarding approval of the protocol including version number and date, ICF (including version and date) and other adjunctive participant material.
  4. List of voting REB members
  5. Signed Clinical Trial Agreement
- REB approvals and notifications: According to the local requirements, the Investigator must have all necessary approvals, including written approval from the REB of the clinical site or other accepted REB prior to enrolling participants in the study. A copy of the written approval must be provided to the Sponsor.
  - Serious Adverse Event (SAE) reports as well as annual and final reports will be submitted to the REB as required.
- Obtaining informed consent: A member of the study team, who is not part of the patient's circle of care, will obtain informed consent in accordance with the procedure described in this study protocol and the requirements of the REB.

- Medical care of participants
- Reporting requirements
- Audits / Inspections: In the event that audits/inspections are initiated by the Sponsor (or its designee) or national/international regulatory authorities, the Investigator must allow access to the original medical records and must provide all requested information. In the event that audits are initiated by regulatory authorities, the Investigator will immediately notify the Sponsor.

## 9.5 Clinical Monitoring

The Sponsor will be responsible for ensuring that adequate monitoring at each site is completed to ensure protection of the rights of participants, the safety of participants, and the quality and integrity of the data collected and submitted. Each clinical site will be monitored according to the study monitoring plan to ensure to verify that:

- The rights and well-being of the participants are protected
- The reported study data are accurate, complete and verifiable from source documents
- The conduct of the study is in compliance with the currently approved CIP/ amendment(s), GCP, the applicable regulatory requirement(s) and applicable requirements of the REB
- There is adequate participant enrollment
- Investigational device accountability (if applicable) is maintained

Monitoring visits will be performed remotely or onsite by qualified Sponsor representatives and will include, but not limited to, the following:

- Verification of the protocol adherence
- Source documentation verification and accuracy of the eCRFs
- Verification that informed consent was obtained for all participants participating in the study in accordance with requirements described in the study protocol
- The safety status of all participants (i.e. (S)AEs/(S)ADEs/DD)
- Verification of completeness of the Site File
- Verification of accuracy of all study logs such as the Delegation of Authority Log, etc.
- Compliance with applicable regulations
- Identification and action to resolve any issues or problems with the study.

At the end of each visit the Monitor will meet with the PI and study site personnel to discuss any relevant findings. Failure by the PI/site staff to address adequately issues of non-compliance may cause the Sponsor to put the Investigator or Site on probation or to withdraw the Investigator/Site from the study. The frequency of monitoring will be based upon

considerations such as enrollment levels, study duration, compliance, or suspected data inconsistency requiring further investigation.

## **9.6 Source Documentation**

Regulations (Health Canada MDR; ISO 14155) require that Investigators maintain information in the participant's medical records that corroborate data collected in the eCRF. In order to comply with these regulatory requirements, at minimum, the following is a list of information that should be maintained and made available as required by monitors and/or regulatory inspectors:

1. Medical history/physical condition relevant to the inclusion/exclusion criteria
2. Dated and signed notes on the day of entry into the study, protocol number, clinical site participant number assigned and a statement that informed consent was obtained and is on file in the participant medical chart
3. Adverse events reported and categorized as Serious Adverse Device Effects (SADEs) their resolution, including supporting documents such as discharge summaries and lab results

The Investigator and the head of the medical institution (where applicable) agree to allow the Clinical Monitor direct access to all relevant documents.

## **9.7 Data Handling**

All eCRF information, study records, reports, and source documents that support the eCRF must be retained in the files of the responsible Investigator according to national requirements following notification by the Sponsor or designee that all investigations have been completed, and will further be retained in accordance with local and international guidelines as identified in the Investigator Site Agreement. This documentation must be accessible upon request by international regulatory authorities or the Sponsor (or designee). The Sponsor or designee must approve archiving or transfer of the documentation for relocation purpose of premises, in writing, prior to the actual file transfer. The Investigator must notify the Sponsor, in writing, of transfer location, duration, and the procedure for accessing study documentation. The Investigator must contact the Sponsor, or designee, in writing at least 30 days before the transfer location, duration, procedure for accessing study documentation or destruction of any records and reports pertaining to the study to ensure they no longer need to be retained.

If the Investigator retires, relocates, or for other reasons withdraws from assuming primary responsibility for keeping the study records, custody per written notice must be submitted to the Sponsor, or designee, indicating the name and address of the person accepting primary responsibility. The REB must be notified in writing of the name and address of the new custodian.

Data will be retained by the Sponsor for 15 years after the end of the study; or, where the investigational device is subsequently placed on the market, for 15 years after the last device has been placed on the market. Clinical data are to be retained by the study site in conformance with regional medical practice requirements.

All clinical study information will be recorded, handled and stored in a way that allows its accurate reporting, interpretation and verification. Data are to be submitted promptly via eCRF after collection. Missing or unclear data will be corrected as necessary throughout the study. The Sponsor will request further documentation such as physician a procedure notes when complications or malfunctions are observed and reported. During monitoring visits, the findings from the review of source documents will be discussed with the Investigator.

All documents shall be maintained in a secure location, protected from unauthorized access or damage, and they shall be archived as per local requirements.

